### 3.3.4 Electrocardiograms

The outcome of the overall evaluation is to be recorded as normal/abnormal in the electronic case report form (eCRF) by the investigator/authorized delegate, with any abnormalities being recorded as not clinically significant or clinically significant.

## 3.4 Pharmacokinetic variables

Blood samples (processed to serum) for pharmacokinetic assessments will be collected from all patients at baseline prior to benralizumab administration at Day 1 and Week 8, at EOT visit (Week 20) or IPD visit and at the Week 28 follow-up visit.

## 3.5 Immunogenicity variables

Immunogenicity assessments will be collected in a similar schedule as the pharmacokinetic assessments.

These will be handled using the visit windowing described in Section 2.2.2. The proportions of patients with ADA results will be presented together with descriptive statistics of the ADA titers.

The presence of neutralizing ADA (nAb) will be tested in ADA-positive samples and the proportions of patients with nAb results will be summarized.

## 4. ANALYSIS METHODS

### 4.1 General principles

The data analyses will be conducted using the SAS® System version 9.2 or above (SAS Institute Inc., Cary, NC). All SAS® programs used to generate analytical results will be developed and validated according to AstraZeneca SAS® programming standards.

Summary data will be presented in tabular format. Categorical data will be summarized by the number and percentage of patients in each category. Continuous data will be summarized by descriptive statistics including N, mean, standard deviation (SD), median, and range. For PK data, in addition, geometric mean and coefficient of variation (CV%) based on log-transformation will be presented. All data will be listed. Data listings will be sorted by patient number.

There are no formal statistical hypotheses to be tested in this study.

## **4.2 Analysis methods**

### **4.2.1 Patient disposition**

Patient disposition will be summarized using the all patients analysis set. The total number of patients will be summarized for the following groups: those who enrolled, those who entered run-in, and those who did not receive treatment after they have been enrolled. The number and percentage of patients within each treatment group will be presented by the following categories; enrolled, received treatment with study drug, did not receive treatment with study drug (and reason), completed treatment with study drug, and withdrawn from study (and reason).

The number of patients enrolled by country and center will be summarized for the FAS.

### **4.2.2 Demographics and patient characteristics**

Demography data such as age, sex, race, and ethnicity will be summarized for the all patients in the FAS. Age will be derived from the date of informed consent-date of birth, rounded down to the nearest integer. For patients in country where date of birth is not recorded the age as recorded in the eCRF will be used.

Descriptive statistics will be presented for the following demographic data:

- Age
- Age group ( $\geq 18$ -<50 years,  $\geq 50$ -<65 years or  $\geq 65$  years)
- Sex (Male, Female)
- Race (White, Black or African American, Asian, native Hawaiian or other Pacific islander, American Indian or Alaska native, Other)
- Ethnicity (Hispanic or Latino, Not Hispanic or Latino)

Descriptive statistics will be presented for the following baseline characteristics:

- Height (cm)
- Weight (kg)

- BMI (kg/m^2)
- BMI group (Normal: ≤25, Overweight: >25 – 30, Obese: >30-35, Morbidly obese: >35)

Various disease related baseline characteristics will also be summarized for the FAS. These include respiratory disease characteristics such as asthma duration, the number of exacerbations in the previous 12 months, and the number of exacerbations requiring hospitalizations in the previous 12 months.

#### **4.2.3 Prior and concomitant medications**

A medication will be regarded as prior if it was stopped on or before the first IP dose date (ie, medication stop date ≤first IP dose date).

A medication will be regarded as concomitant if the start date is after the first IP dose date, but prior to the end of treatment period, or if it started prior to the first IP dose date and was ongoing after the first IP dose date.

The number and percentage of patients who take prior medications, those who take allowed concomitant medications, and those who take disallowed concomitant medications during the study, will be presented for the FAS. Prior and concomitant medications will be classified according to the AZDD. The summary tables will present data by anatomical therapeutic chemical (ATC) classification category and generic term.

All prior and concomitant medications will be listed.

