##### **3.5.1.1 Background medication**

Background asthma medications may be increased from Visit 2 through 8 at the discretion of the Investigator to improve the patient's asthma control, if needed. If the addition of a new asthma controller therapy or a change in dose of any asthma medication(s) is judged by the Investigator as necessary, the justification should be documented in the source and in the eCRF.

A step down in therapy is discouraged and must be discussed beforehand with the AstraZeneca Study Physician.

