#### **2.2.1 Important protocol deviations**

Important deviations will be those which are considered to potentially impact upon the interpretation of the primary endpoint in the study. Only important protocol deviations will be listed and tabulated in the CSR.

The following categories of protocol deviations will be reviewed by medical advisors and statisticians prior to database lock to determine those which are considered important deviations as outlined above.

- Patients who do not meet the inclusion criteria
- Patients who meet any of the exclusion criteria
- Concomitant use of disallowed medications (to be identified through programming)
- Patients who developed withdrawal criteria during the study but were not withdrawn

Patients for whom a significant protocol deviation was recorded that impacts the interpretation of the study safety outcomes will have a footnote added to applicable output to describe the deviation and its potential impact. Such patients will be identified as part of the protocol deviation review process, prior to database lock.

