## **3.2 Secondary outcome variable**

### **3.2.1 Asthma Control Questionnaire-6**

The Asthma Control Questionnaire-6 (ACQ-6) is a shortened version of the ACQ that assesses asthma symptoms (nighttime waking, symptoms on waking, activity limitation, shortness of breath, wheezing, and short-acting  $\beta_2$  agonist use) omitting the forced expiratory volume in 1 second (FEV1) measurement from the original ACQ-7 score.

Patients are asked to recall how their asthma has been during the previous week by responding to 1 bronchodilator use question and 5 symptom questions. Questions are weighted equally and scored from 0 (totally controlled) to 6 (severely uncontrolled). The mean ACQ-6 score is the mean of the responses. The mean score will be missing if any symptom score is missing.

The questionnaire will be completed at the study center at Weeks -2, 0, 4, 8, 12, 16, 20 and IPD.

The outcome variable for ACQ-6 will be the change in mean score from baseline (Week 0) to each of the post-treatment periods. There will be no imputation for missing values.

Asthma control responder status will be evaluated as a supportive analysis. Patients will be categorized according to the following limits (Juniper et al 2005), at the end of treatment, where end of treatment is defined as week 20 (EOT visit):

- $ACQ-6 (EOT - baseline) \leq -0.5 \rightarrow$  Improvement
- $-0.5 < ACQ-6 (EOT - baseline) < 0.5 \rightarrow$  No change
- $ACQ-6 (EOT - baseline) \geq 0.5 \rightarrow$  Deterioration

An ACQ-6 responder will be defined as a patient who had improvement on ACQ-6, ie, an ACQ-6 responder variable takes value 1 if change from baseline to end of treatment in  $ACQ-6 \leq -0.5$  and 0 otherwise. Patients with missing or non-evaluable ACQ-6 data at end of treatment visit will be considered non-responders.

Additionally, patients will be categorized according to their ACQ-6 defined asthma control status at the end of treatment using the following score thresholds (Juniper et al 2006):

- $ACQ-6 (EOT) \leq 0.75 \rightarrow$  Well controlled
- $0.75 < ACQ-6(EOT) < 1.5 \rightarrow$  Partly controlled
- $ACQ-6 (EOT) \geq 1.5 \rightarrow$  not well controlled

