### **3.3.1 Adverse events**

Adverse events (AEs) experienced by the patients will be collected throughout the entire study and will be coded using the latest version of the Medical Dictionary for Regulatory Activities (MedDRA) per the Data Management Plan.

Adverse event data will be categorized according to their onset date into the following study periods:

- AEs in the on-study period are defined as those with onset between day of the first dose of study treatment and scheduled follow-up visit, inclusive.
- AEs in the on-treatment period are defined as those with onset between day of first dose of study treatment and scheduled EOT for patients who complete study treatment or scheduled IPD visit for those patients who prematurely discontinue study treatment, inclusive. In the event that the EOT or IPD visit is beyond the protocol defined visit window, AEs with onset after the last dose of study treatment date+28 days+3 days (visit window) will be excluded from the on-treatment period and instead assigned to the post-treatment period.
- AEs in the post-treatment period are defined as those with onset after, but not including, the EOT visit (or the IPD visit) up to and including follow-up visit.

For instances where a patient attends the safety follow-up visit only, but does not attend an earlier IPD visit or EOT visit, AEs occurring on or after the day of the first dose of study treatment and on or before the last dose of study medication +28 days will be assigned to the on-treatment period, while AEs with onset date after this time will be assigned to the post-treatment period.

Adverse event on-study period is a combined period of on-treatment period and post-treatment period (when applicable).

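### SAP 4.2.3 leaves a drug started on the first dose date either unclassified or always counted as prior, even when it was given after the injection

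*SAP*

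**What the plan says.** SAP 4.2.3 sets three date rules. The prior rule is "A medication will be regarded as prior if it was stopped on or before the first IP dose date", and a note in the same sentence confirms that equality with the first dose date counts as prior. A drug is "concomitant if the start date is after the first IP dose date, but prior to the end of treatment period", or it is concomitant "if it started prior to the first IP dose date and was ongoing after the first IP dose date". None of the rules uses time of day. The section then tabulates patients with prior medications, with allowed concomitant medications, and "those who take disallowed concomitant medications during the study, will be presented for the FAS".

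Other sections bear on these rules:

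- SAP 3.3.1 defines on-treatment adverse events as "those with onset between day of first dose of study treatment and scheduled EOT for patients who complete study treatment", with both ends included and the IPD visit replacing EOT for early discontinuation.
- SAP 2.2.1 lists among the deviations to be reviewed "Concomitant use of disallowed medications (to be identified through programming". It does not say what concomitant means there.
- SAP 4.2.3 does not define the end of the treatment period. The nearest definition is for ACQ-6 in SAP 3.2.1: "at the end of treatment, where end of treatment is defined as week 20 (EOT visit".
- SAP 4.2.4 separately summarises maintenance asthma, ICS and OCS medications.
- Protocol 3.5.1.1: "Background asthma medications may be increased from Visit 2 through 8 at the discretion of the Investigator". Visit 2 is the first dose visit.
- Protocol 6.6 and 6.7 call for at least 2 hours of observation after dosing, and for drugs to treat acute reactions to be at hand.

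**The concern.** Both concomitant limbs exclude a start on the first dose date, while the prior rule takes in anything that stopped on it. That day is each patient's first exposure to benralizumab, and the protocol itself foresees new medication then, either for an acute reaction or as a change to asthma therapy.

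The adverse event and medication tables could then disagree about one event. SAP 3.3.1 places a Day 1 reaction in the on-treatment period. The single dose that treated it would be tabulated as taken before study drug, and a course begun that day would not be tabulated as prior or concomitant at all. Two programmers could also fill the gap differently.

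**Working it through.** The plan gives no figure to reproduce, so the check is one of date logic on complete dates.

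**Inputs.** The first dose date is Day 1 (SAP 2.2.2). Week 20 EOT is 20 × 7 + 1 = Day 141, and the Week 28 follow-up is 28 × 7 + 1 = Day 197, both as in the SAP window tables. I take the end of treatment in SAP 4.2.3 to be EOT. That is an assumption, and it does not affect the Day 1 results.

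**Rules as written.** Prior: stop ≤ 1. Concomitant: 1 < start < 141, or start < 1 and stop > 1.

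| Start | Stop | Class under SAP 4.2.3 |
|---|---|---|
| before Day 1 | on or before Day 1 | prior |
| before Day 1 | after Day 1 | concomitant |
| Day 1 | Day 1, taken before the injection | prior (correct) |
| Day 1 | Day 1, taken after the injection | prior (wrong) |
| Day 1 | after Day 1, or ongoing | none |
| Days 2 to 140 | any | concomitant |
| Day 141 or later | any | none |

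I ran every start day from −14 to 197 with every stop day up to 197, plus ongoing use. The only unclassified combinations were those starting on Day 1 and continuing (196 stop days plus ongoing = 197) and those starting on or after Day 141 (1,710). No combination fell in two classes. These are possible date pairs, not patients or records.

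**Comparison with adverse events.** The on-treatment period in SAP 3.3.1 includes Day 1 and the EOT day. The concomitant window excludes both as start dates.

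**Reach of the restrictions.** Protocol 3.5.2.1 bars some asthma medications from enrolment through the whole study. Protocol 3.5.2.2 bars live vaccines from 30 days before Visit 2 until 16 weeks after the last dose. With the last dose at Week 16 (Day 113), that is 113 + 112 = Day 225, past the follow-up visit.

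**Check of the proposed rule.** I coded the rule given under the fix, with the optional post-treatment category, and tried start days −90 to 197 with every stop day and ongoing use. Day 1-only drugs were tried as known pre-injection, known post-injection and unknown order. Every case fell in exactly one class.

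**The case against.** The strongest reply is that little depends on this. The study is open-label, has one arm and tests no hypothesis. SAP 4.1 says that all data will be listed, so the records stay visible. The most foreseeable continuing Day 1 start, a change in maintenance asthma therapy, may still appear under SAP 4.2.4. Protocol 6.7 requires reaction drugs to be available, which says nothing about how often they would be used. All of this stands and sets the weight of the point. It does not repair the rule: SAP 4.2.4 covers only maintenance asthma, ICS and OCS drugs, and a listing does not correct a table. Neither the SAP amendment history nor SAP section 6 mentions the matter.

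Three stronger readings are tempting, and the documents do not support them.

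- *The disallowed count wrongly omits drugs first taken after EOT.* SAP 4.2.3 has just bounded concomitant by the treatment period, so this is mainly a choice of scope under a loose label. Drugs started before EOT and continued into follow-up are still counted.
- *Disallowed drugs started on Day 1 will escape deviation review.* This follows only if the SAP 2.2.1 program reuses the SAP 4.2.3 definition, which neither document says. Important deviations are also those that could affect interpretation of the primary endpoint, and the primary endpoints concern administration and device function.
- *The size can be read from the number of uncovered days.* Calendar days say nothing about how many records or patients fall on them.

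**Conclusion.** The point holds as a minor error of definition. As written, SAP 4.2.3 gives no class to a drug started on the first dose date and continued, and it tabulates as prior a drug given after the injection and stopped the same day. The consequence is wrong counts in descriptive medication tables, and possibly in the programmed deviation check if it shares the definition. The documents do not allow the number of affected records to be calculated; it is probably small. Primary endpoints, adverse event summaries and listings are unaffected.

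The conclusion assumes that the date rules are programmed literally. The mismatch between the label on the disallowed count and its period is a secondary wording point.

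**What to change.** Reword SAP 4.2.3:

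- **Prior:** stopped before the first IP dose date; or started before that date and stopped on it; or started and stopped on that date where the record shows use before the injection (for example, the bronchodilator for Visit 2 reversibility testing).
- **Concomitant:** started on or after the first IP dose date, up to and including the EOT or IPD visit, apart from the Day 1-only pre-injection drugs above; or started before the first IP dose date and ongoing after it. A Day 1-only drug of unknown order is concomitant.
- **Label:** rename the disallowed count so that it refers to the treatment period, or add a category for starts after EOT/IPD up to the follow-up visit. Relabelling is simpler. Extending the count to follow-up would still not match restrictions that run from enrolment or to 16 weeks after the last dose.
- **Deviation check:** state that the program in SAP 2.2.1 uses the same definition.

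The cost is SAP wording and minor programming, plus a look at the record for drugs taken only on Day 1. Protocol 3.5.1 already collects the reason for treatment. Two imperfections remain: a few pre-injection Day 1 drugs of unknown order will count as concomitant, and a drug started earlier and last taken on Day 1 stays prior even if that last use followed the injection.

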#### **4.2.4 Maintenance asthma/inhaled corticosteroids/oral corticosteroids medications**

Maintenance asthma medications, maintenance inhaled corticosteroid (ICS) medications and maintenance oral corticosteroid (OCS) medications will be summarized for the FAS by ATC and preferred term (PT).

#### **4.2.5 Medical history, past and current,-not respiratory**

Medical history will be coded using the latest MedDRA version.

Relevant medical conditions will be summarized by system organ class (SOC) and PT for the FAS.

A separate summary will be presented for past and current conditions.

Medical history data will be fully listed.

#### **4.2.6 Surgical history**

Surgical history will be coded using the latest MedDRA version.

Relevant surgical procedures will be summarized by SOC and PT for the FAS.

Surgical history data will be fully listed including a Yes/No for any current medication taken for the surgical procedures.

#### **4.2.7 Lung function data at baseline**

Descriptive statistics will be presented for the FAS for the following lung function data: Pre-bronchodilator (Pre-BD) lung function data (FEV1 [L], FEV1 [% PN], FVC [L], FVC [% PN] and FEV1/FVC) and post-bronchodilator data (FEV1 reversibility [%]).

All lung function data will be fully listed.

#### **4.2.8 Primary outcome variables**

##### **4.2.8.1 Primary analyses**

For each of the primary endpoints in Section 3.1, the data will be summarized along with their corresponding exact 95% confidence interval estimates (Clopper-Pearson method).

In addition, the proportion of AI used to administer benralizumab at home or in the clinic will also be summarized by the malfunction reasons (Product Complaints).

All data from the administration related questionnaire will be listed by patient and visit.

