## 2. STUDY OBJECTIVES

### 2.1 Primary objective

Primary objective	Outcome measure
To assess patient- or caregiver-reported functionality and reliability of the benralizumab single-use auto-injector (AI) device in an at-home setting and performance of the AI device after use.	
 
• Proportion of patients/caregivers who successfully administered benralizumab 30 mg subcutaneously (SC) by injection with an AI device at home
 
• Proportion of returned AI devices used to administer benralizumab at home that have been evaluated as functional
 
• Proportion of AI device used to administer benralizumab at home or in the clinic and have been reported as malfunctioning (Product Complaints)
 

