For Visit 2 through Visit 4, all study procedures must be done on the scheduled day of IP injection. Urine pregnancy tests must be done prior to IP administration at Visits 2 (Week 0), 3 (Week 4), and 4 (Week 8). At-home urine pregnancy tests are to be done by WOCBP prior to IP administration at Weeks 12 and 16 and repeated by the study center staff at Visits 5 and 6. In the case of a positive test, the patient is NOT to administer IP and is to call the study center. Urine pregnancy tests will be done at the study center at the EOT visit (Week 20) and the Follow-up visit (Week 28).

The same person must administer the IP during the entire study, whether it is the patient or caregiver.

Restrictions as set out in Section 3.5.2 will continue to apply throughout the treatment period. In case of asthma worsening/exacerbation (see Section 7.3.7), patients should be evaluated at the study center when feasible.

Patients will return to the study center at Week 20 for the EOT visit and at Week 28 for a Follow-up visit. If the IP was administered by a caregiver, the caregiver must accompany the patient to these visits.

For premature discontinuation please refer to Section 3.6.

Completion or early termination of the treatment will be registered via IWRS/IVRS for each patient.

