### **6.5.1.2 Single Use Auto-Injector malfunction**

An AI device malfunction is when the AI device appears normal during verification of shipment and then does not work during administration, e.g., the autoinjector activated prematurely, the autoinjector stalled or did not expel the full volume, needle guard safety feature did not deploy or remain locked, glass syringe breakage, needle bent or broke upon use. Device malfunctions should be reported using the Device Malfunction Return Instruction and the Study Monitor should be notified.

Site staff will be asked to send back malfunctioning devices to the depot or local sponsor company according to local procedures. Address and attention for malfunctioning device is available in the Device Malfunction Return Instruction.

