## **8.4 Variables for analyses**

### **8.4.1 Calculation or derivation of primary endpoints**

#### **8.4.1.1 Primary endpoints**

The primary endpoints are as follows:

- Proportion of patients/caregivers who successfully administered benralizumab with an AI device at home among those who have been deemed by the Principal Investigator to be suitable for at-home administration and are still in the study at Week 12 or Week 16. A successful administration is defined as an injection completed, an answer of

“Yes” to all 5 questions in the administration questionnaire (see Appendix G), and the autoinjector adequately passed the visual inspection and functional tests.

Patients/caregivers who are unwilling to self-administer at Week 8 will not be considered as failures, but will be counted as unsuitable for at-home administration and follow the premature IP Discontinuation (IPD) procedure.

- Proportion of returned AI devices used to administer benralizumab at home that have been evaluated as functional among all returned AI devices used to administer benralizumab at home. A functional AI device is defined as an answer of “Yes” to all the questions in the visual inspection and function tests. Devices that are not returned for evaluation will be excluded from analysis.
- Proportion of returned AI devices used to administer benralizumab at home and in the clinic that have been reported as malfunctioning (Product Complaints).

The first 2 endpoints above will be calculated at Weeks 12 and 16, while the third endpoint will be obtained at each of the post-treatment periods (Weeks 0, 4, 8, 12, and 16).

In addition, the following variables will be calculated among all patients/caregivers who have been deemed by the Investigator to be suitable for at-home administration at Week 8 and are still in the study at Week 16:

- Proportion of patients/caregivers who successfully administered benralizumab with an AI device at both Weeks 12 and 16, and
- Proportion of patients/caregivers who returned an AI device used to administer benralizumab at home and evaluated as functional at both Weeks 12 and 16.

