## **8.5 Methods for statistical analyses**

The analysis of the primary endpoints will include all data captured during Weeks 12 and 16 (for Product Complaints with addition of Weeks 0, 4 and 8) while secondary endpoints will include all data captured during the 20-week treatment period, and up to follow-up (where applicable), unless the patient withdraws consent to study participation, regardless of whether study treatment was prematurely discontinued, or delayed, and/or irrespective of protocol

adherence. All efficacy analyses will be performed using an Intent-to-Treat (ITT) approach based on the FAS. For consistency, demographic and baseline characteristics will be presented using FAS. Safety objectives will also be analyzed using the FAS.

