## **1.2 Study design**

This is an open-label study designed to assess patient- or caregiver-reported functionality, performance, and reliability of an AI with a fixed 30 mg dose of benralizumab administered SC in an at-home setting.

Approximately 120 patients, 18 to 75 years of age, globally with severe asthma will enter the treatment period to receive 5 SC doses (Week 0, Week 4, Week 8, Week 12, and Week 16) of benralizumab.

Following a 2-week screening period, eligible patients will receive 3 SC doses of 30 mg of benralizumab at the study site (Week 0, Week 4, and Week 8). At Week 0, the Principal Investigator (PI) or his/her designee will administer the study drug. At Week 4, the patient or caregiver will have the option of administering the study drug under site supervision to ensure they understand the procedure and are capable of doing so. At Week 8, the patient or caregiver will have to perform the injection, again under site staff supervision. Patients or caregivers unable or unwilling to administer investigational product (IP) at this visit will be discontinued from the study.

The patient or caregiver will be given the Instructions for Use (IFU) to refer to for home administrations. The final 2 doses of benralizumab (Week 12 and Week 16) will be self-administered by the patient or administered by the caregiver at home. After each of these administrations, the patient will return for a scheduled on-site visit within 48 hours.

For the at-home administrations, whether the patient is self-administering or the caregiver is administering to a patient, that person administering the dose will fill out a questionnaire designed to indicate whether the device functioned correctly and the dose was successfully administered. Both the completed questionnaire and the used device are to be returned to the site during each of the clinic visits (Visit 5 [Week 12] and Visit 6 [Week 16]). The site is to subsequently return the used devices and questionnaires to the Sponsor for evaluation.

An end-of-treatment (EOT) visit will be performed at Week 20 and a follow-up visit at Week 28 (12 weeks after last IP administration).

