## **3. PRIMARY AND SECONDARY VARIABLES**

### **3.1 Primary outcome variables**

Three primary endpoints will be evaluated in this study as follows.

- Proportion of patients/caregivers who successfully administered benralizumab 30 mg SC by injection with an AI at home.

The proportion will be calculated among all patients/caregivers who have been deemed by the Principal Investigator to be suitable for at-home administration and are still in the study at the time of benralizumab injection at Week 12 or Week 16. Patients who are still in the study is defined as patients who had been treated for the specified time point. A successful administration is defined as an injection completed, an answer of “Yes” to all 5 questions in the Questionnaire, and adequately passed the visual inspection and function tests. Patients/caregivers who are unwilling to self-administer at Week 8 will not be considered as

failures, but will be counted as unsuitable for at-home administration and follow the premature IP Discontinuation (IPD) procedure.

- Proportion of returned AI used to administer benralizumab at home that have been evaluated as functional among all returned AI used to administer benralizumab at home.

A functional AI is defined as an answer of “Yes” to all the questions in the visual inspection and function tests. Devices that are not returned for evaluation will be excluded from analysis.

- Proportion of AI used to administer benralizumab at home or in the clinic and have been reported as malfunctioning (Product Complaints).

The first 2 endpoints above will be calculated at Weeks 12 and 16, while the third endpoint will be calculated at Week 0, 4, 8, 12 and 16 as well as for the overall study period (from Week 0 to Week 16), the in-clinic administration period (from Week 0 to Week 8) and the at-home administration period (from Week 12 to Week 16).

In addition, the following variables will be calculated among all patients/caregivers who have been deemed by the Investigator to be suitable for at-home administration at Week 8 and are still in the study at Week 16:

- Proportion of patients/caregivers who successfully administered benralizumab with an AI at both Weeks 12 and 16
- Proportion of patients/caregivers who returned an AI used to administer benralizumab at home and evaluated as functional at both Weeks 12 and 16.

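### The pooled Weeks 0–16 malfunction proportion is given an exact 95% interval that is exact only if devices used by the same person fail independently (minor)

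*SAP*

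**What the plan says.** The unit of the third primary endpoint is the device. Protocol 2.1 defines it as "Proportion of AI device used to administer benralizumab at home or in the clinic and have been reported as malfunctioning (Product Complaints".

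Protocol 8.4.1.1 lists weekly values: "the third endpoint will be obtained at each of the post-treatment periods (Weeks 0, 4, 8, 12, and 16". SAP 3.1 adds pooled ones: "the third endpoint will be calculated at Week 0, 4, 8, 12 and 16 as well as for the overall study period", and also for the in-clinic period (Weeks 0–8) and the at-home period (Weeks 12–16). The pooling fits the protocol's objective and its analysis section, which defines the data for this endpoint as Weeks 12 and 16, "for Product Complaints with addition of Weeks 0, 4 and 8". The pooling itself is therefore not the problem.

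SAP 4.2.8.1 attaches the interval: "the data will be summarized along with their corresponding exact 95% confidence interval estimates (Clopper-Pearson method". It does not distinguish single-week from pooled proportions.

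On who injects, SAP 1.2 has site staff give Week 0. Then "At Week 4, the patient or caregiver will have the option of administering the study drug under site supervision". From Week 8 the patient or caregiver must inject. Protocol 4.2 adds: "The same person must administer the IP during the entire study, whether it is the patient or caregiver".

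**The concern.** Clopper-Pearson limits guarantee their nominal coverage when the count is binomial, that is, when devices fail independently with a common probability. A completer supplies five devices to the Weeks 0–16 proportion. The same patient or caregiver operates three of them, or four after taking the Week 4 option. If some users are more likely than others to report a malfunction, reports cluster, the count varies more than a binomial count, and the interval is too narrow.

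A route to clustering exists on paper. Protocol 6.5.1.2 counts as a malfunction that "the autoinjector stalled or did not expel the full volume". Protocol 5.1.3 describes a user lifting the device before the injection is complete, which could produce the same report at more than one dose. Neither document mentions repeated devices per patient or any adjustment for them.

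What is at stake is the precision claimed for the overall device-failure rate, a primary-endpoint result.

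**Working it through.** **Inputs from the documents.** About 120 patients treated and about 100 completing (Protocol 8.2, SAP 1.3); five doses; staff inject at Week 0, the user may inject at Week 4 and must at Weeks 8, 12 and 16; two-sided 95% Clopper-Pearson.

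**Assumptions, not in the documents.** Even loss to 100 completers gives 120 + 115 + 110 + 104 + 100 = 549 devices. The true malfunction rate is 1–5%, with 0.1–1% as a second range. The ICC is 0, 0.1 or 0.2. Week 4 opt-in is 0, 50 or 100%. Staff-given devices are independent, and dropout is unrelated to malfunction.

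**Step 1: user clusters.** Staff-given devices stand alone. A user's own devices form a cluster of size m.

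| Week 4 opt-in | Singles | Pairs | Triples | Quadruples | Devices |
|---|---|---|---|---|---|
| 0% | 241 | 4 | 100 | 0 | 241 + 8 + 300 = 549 |
| 50% | 183 | 5 | 52 | 50 | 183 + 10 + 156 + 200 = 549 |
| 100% | 125 | 6 | 4 | 100 | 125 + 12 + 12 + 400 = 549 |

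**Step 2: variance inflation.** Design effect = 1 + ICC × Σm(m−1)/549. The sums are 608, 922 and 1236 for 0, 50 and 100% opt-in. At ICC 0.1 the design effect is 1.11, 1.17 and 1.23; at ICC 0.2 it is 1.22, 1.34 and 1.45.

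**Step 3: exact coverage.** Each cluster is beta-binomial with mean p and the given ICC. The distribution of the total is obtained by convolution, without simulation. Coverage is the probability that the Clopper-Pearson limits computed on 549 devices contain p, averaged over p from 1% to 5% in steps of 0.05 points.

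| ICC | 0% opt-in | 50% | 100% |
|---|---|---|---|
| 0 | 96.4% | 96.4% | 96.4% |
| 0.1 | 95.3% | 94.8% | 94.2% |
| 0.2 | 94.2% | 93.1% | 91.9% |

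The first row reproduces the plan's stated level: with independent devices the 95% is met with some margin. At ICC 0.1 the average runs from 0.3 points above nominal to 0.8 below. At ICC 0.2 the shortfall is 0.8, 1.9 and 3.1 points. Averaged over rates of 0.1–1%, coverage is at least 95.3% at all three ICCs and every opt-in.

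**Step 4: scale of the ICC.** The chance that a given later device of a user is also reported, once one has been, is p + ICC(1 − p). At p = 2% this is 0.02 + 0.1 × 0.98 = 11.8% at ICC 0.1, and 0.02 + 0.2 × 0.98 = 21.6% at ICC 0.2.

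**Step 5: one data set.** Suppose 11 of 549 devices malfunction (2.0%). Clopper-Pearson gives 1.0–3.6%. For the clustered interval, with y reports among the m devices of each of K = 120 patients, v = K/(K−1) × Σ(y − p̂m)²/549². The effective number of devices is p̂(1−p̂)/v × (t with 548 df / t with 119 df)², capped at 549. The example takes all reports from completers and no patient with more than two.

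| Patients behind the 11 reports | Clustered interval | Probability if devices are independent |
|---|---|---|
| 11 | 1.0–3.6% (cap applies) | 67% |
| 10 | 1.0–3.7% | 28% |
| 9 | 0.9–3.9% | 4% |
| 8 | 0.8–4.0% | 0.3% |

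**The case against.** The strongest reply is that no recurrence has been shown and the documents work against it. Every dose uses a new device. A failure with no observable defect may be classed as use error (Protocol 5.1.3), which can filter out the early-removal route. Weeks 4 and 8 are supervised. Users who become unwilling or unable to inject are discontinued (Protocol 3.6). With an ICC near zero the planned interval is slightly conservative. Nothing is tested, all data are listed, and malfunctions are tabulated by reason, so a reader could find repeat reports. All of this stands. It limits the size of the point but does not supply the independence that the word exact relies on.

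Three stronger readings are tempting.

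- **All five devices of a patient share the correlation.** The average shortfall over 1–5% would then be about 2.4 points at ICC 0.1 and 6.3 at ICC 0.2. The documents do not support this as a within-user effect, because staff operate the Week 0 device and may operate the Week 4 one.
- **The interval does under-cover.** Any shortfall comes from an assumed rate, ICC and opt-in, and at low rates there is none on average.
- **Single-week intervals are wholly safe.** They hold one device per patient, so the repeat-device problem is absent. But if one staff member injects several patients at a site, Week 0 devices could be correlated. As an illustration, with about 30 centers of four patients each, a 5% rate and ICC 0.1, Week 0 coverage would be 93.9%; at 1–2% it stays above 95%. The documents do not show that this occurs.

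**Conclusion.** The point holds, and it is minor. The plan labels the pooled Weeks 0–16 interval exact although three or four of a completer's devices come from one user and neither document addresses that dependence. On the stated assumptions (549 devices, independent staff-given devices, rates of 1–5%), the average loss of coverage is at most 0.8 points at ICC 0.1 and 0.8 to 3.1 points at ICC 0.2, depending on Week 4 opt-in. At ICC 0, or at rates of 0.1–1% with ICC up to 0.2, there is no average loss. The rate, ICC and opt-in are all assumed. No conclusion of the trial turns on this interval.

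**What to change.** Keep Clopper-Pearson for the single-week proportions. For the pooled Weeks 0–16 proportion, specify in SAP 4.2.8.1:

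- a Clopper-Pearson interval on the effective number of devices with the patient as cluster (Korn-Graubard, including its degrees-of-freedom adjustment);
- a cap at the actual number of devices;
- plain Clopper-Pearson when there are no malfunctions.

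Report beside it the number of patients with at least one malfunction, noting that patients contribute one to five devices. Applying the same rule to the two sub-periods is optional. A patient-level percentile bootstrap is not a good substitute: events are few, and with none it collapses to a zero-width interval.

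The cost is one or two SAP sentences and a few lines of code, with no new data. In simulation (40,000 trials per setting; rates 0.5, 1, 2 and 5%), the capped interval kept coverage above 95%. It was about 1–3% wider on average with independent devices. At ICC 0.2 with 50% opt-in it was about 15–17% wider for rates of 1–5%. Clustering by patient does not address any correlation among Week 0 devices given by the same staff.
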